8.5.3.10 Week 8 Visit

The following procedures will be conducted at the Week 8 Visit:

- Physical examination.
- Vital Signs.
- Urine or serum pregnancy test (for female subjects of childbearing potential).
- Blood draws:
 - Creatinine.
 - Serum biochemistry panel.
 - CCI [REDACTED]
 - DSA.
 - C1-esterase inhibitor activity/antigen.
 - Immunoglobulin concentration.
 - CCI [REDACTED]

NOTE: All blood draws should be completed before administration of C1-INH and IVIg.

- Subcutaneous administration of C1-INH (60 IU/kg, dose rounded to the lowest 1 mL).
- Investigational product dispense, if applicable.
- Investigational product vial return, if applicable.
- IVIg begins (2 grams/kg total dose; the dose must be administered over a minimum period of at least 2 days, and may be administered over a period of up to 5 days).
- Adverse events.
- Concomitant therapies.
- Schedule next visit.

8.5.3.11 Week 9 and Week 10 Visits

The following procedures will be conducted at the Week 9 and 10 Visits:

- Blood draws:
 - Creatinine.
 - Serum biochemistry panel.
 - C1-esterase inhibitor activity/antigen (Week 10 only).

NOTE: All blood draws should be completed before administration of C1-INH.

- Subcutaneous administration of C1-INH (60 IU/kg, dose rounded to the lowest 1 mL).
- Investigational product dispense, if applicable.
- Investigational product vial return, if applicable.
- Adverse events.
- Concomitant therapies.
- Schedule next visit.

8.5.3.12 Week 11 Visit

The following procedures will be conducted at the Week 11 Visit:

- Blood draws:
 - Creatinine.
 - Serum biochemistry panel.

NOTE: All blood draws should be completed before administration of C1-INH.

- Subcutaneous administration of C1-INH (60 IU/kg, dose rounded to the lowest 1 mL).
- Investigational product dispense, if applicable.
- Investigational product vial return, if applicable.
- Adverse events.
- Concomitant therapies.
- Schedule next visit.

Subjects who are a part of the **CCI** [REDACTED] will undergo procedures as presented above, but will also have additional blood draws, as presented in [Table 6](#).

CCI
[REDACTED]

8.5.3.13 Week 12 Visit

The following procedures will be conducted at the Week 12 Visit:

- EQ-5D-3L questionnaire.
- Blood draws:
 - Creatinine.

- Serum pregnancy test (for female subjects of childbearing potential).
- Serum biochemistry panel.
- Hematology.
- CCI [REDACTED]
- DSA.
- C1-esterase inhibitor activity/antigen.
- Immunoglobulin concentration.
- CCI [REDACTED]
- CCI [REDACTED]
- Retention sample for viral serology.

NOTE: All blood draws should be completed before administration of C1-INH and IVIg.

- Subcutaneous administration of C1-INH (60 IU/kg, dose rounded to the lowest 1 mL).
- Investigational product dispense, if applicable.
- Investigational product vial return, if applicable.
- IVIg begins (2 grams/kg total dose; the dose must be administered over a minimum period of at least 2 days, and may be administered over a period of up to 5 days).
- Adverse events.
- Concomitant therapies.
- Schedule next visit.

8.5.3.14 Week 13 Visit/End of Treatment Period 1 for Non-responders/Start of Treatment Period 2 for Responders

The following procedures will be conducted at the Week 13 Visit, or if a subject withdraws/discontinues from the study during TP1:

- Physical examination.
- Vital Signs.
- Adverse events.
- Concomitant therapies.
- Responder status, as determined by CSL.

- Randomization of responders to treatment with blinded investigational product (either C1-INH or placebo) in TP2.
- Investigational product dispense, if applicable.
- Subcutaneous administration of C1-INH/placebo (60 IU/kg, dose rounded to the lowest 1 mL) for responders.
- Investigational product vial return, if applicable.
- Schedule next visit.

Early Withdrawal During Treatment Period 1

In addition, for subjects who withdraw/discontinue from the study during TP1, the following blood draws should also be collected:

- Creatinine.
- Serum biochemistry panel.
- Hematology.
- CCI [REDACTED]
- DSA.
- C1-esterase inhibitor activity/antigen.
- Immunoglobulin concentration.
- CCI [REDACTED]
- CCI [REDACTED]
- Retention sample for viral serology.
- Serum pregnancy test (for female subjects of childbearing potential).

8.5.4 Treatment Period 2

Beginning at the final visit in Treatment Period 1 (ie, the Week 13 Visit), and throughout TP2:

- Beginning during TP2, a blood sample for creatinine measurement will be drawn once every 14 days (\pm 7 days) at the study site, at home by a medical professional. The frequency of blood draw for creatinine measurement may occur more frequently at the investigator's discretion.
- Subcutaneous investigational product (ie, C1-INH or placebo) will be administered every 3 or 4 days (ie, twice weekly), as per the randomization schedule.

8.5.4.1 Week 16 Visit

The following procedures will be conducted at the Week 16 Visit:

- Blood draws:
 - Creatinine.
 - Serum pregnancy test (for female subjects of childbearing potential).
 - **CCI** [REDACTED]
 - DSA.
 - C1-esterase inhibitor activity/antigen.
 - **CCI** [REDACTED]

NOTE: All blood draws should be completed before administration of investigational product and IVIg.

- Subcutaneous administration of blinded investigational product (C1-INH [60 IU/kg] or placebo, dose rounded to the lowest 1 mL).
- Investigational product dispense, if applicable.
- Investigational product vial return, if applicable.
- IVIg may begin if DSA is \geq 2000 MFI (2 grams/kg total dose; the dose must be administered over a minimum period of at least 2 days, and may be administered over a period of up to 5 days).
- Adverse events.
- Concomitant therapies.
- Schedule next visit.

8.5.4.2 Week 20 Visit

The following procedures will be conducted at the Week 20 Visit:

- Urine or serum pregnancy test (for female subjects of childbearing potential).
- Blood draws:
 - Creatinine.
 - Serum Biochemistry panel.
 - Hematology.
 - **CCI** [REDACTED]

- DSA.

NOTE: All blood draws should be completed before administration of investigational product and IVIg.

- Subcutaneous administration of blinded investigational product (C1-INH [60 IU/kg] or placebo, dose rounded to the lowest 1 mL).
- Investigational product dispense, if applicable.
- Investigational product vial return, if applicable.
- IVIg may begin if DSA is \geq 2000 MFI (2 grams/kg total dose; the dose must be administered over a minimum period of at least 2 days, and may be administered over a period of up to 5 days).
- Adverse events.
- Concomitant therapies.
- Schedule next visit.

8.5.4.3 Week 24 Visit

The following procedures will be conducted at the Week 24 Visit:

- Physical Examination.
- Vital Signs.
- Urine or serum pregnancy test (for female subjects of childbearing potential).
- Blood draws:
 - Creatinine.
 - CCI [REDACTED]
 - DSA.

NOTE: The blood draw should be completed before administration of investigational product and IVIg.

- Subcutaneous administration of blinded investigational product (C1-INH [60 IU/kg] or placebo, dose rounded to the lowest 1 mL).
- Investigational product dispense, if applicable.
- Investigational product vial return, if applicable.

- IVIg may begin if DSA is \geq 2000 MFI (2 grams/kg total dose; the dose must be administered over a minimum period of at least 2 days, and may be administered over a period of up to 5 days).
- Adverse events.
- Concomitant therapies.
- Schedule next visit.

8.5.4.4 Week 28 Visit

The following procedures will be conducted at the Week 28 Visit:

- Urine or serum pregnancy test (for female subjects of childbearing potential).
- Blood draws:
 - Creatinine.
 - Serum Biochemistry panel.
 - Hematology.
 - CCI [REDACTED]
 - DSA.

NOTE: All blood draws should be completed before administration of investigational product and IVIg.

- Subcutaneous administration of blinded investigational product (C1-INH [60 IU/kg] or placebo, dose rounded to the lowest 1 mL).
- Investigational product dispense, if applicable.
- Investigational product vial return, if applicable.
- IVIg may begin if DSA is \geq 2000 MFI (2 grams/kg total dose; the dose must be administered over a minimum period of at least 2 days, and may be administered over a period of up to 5 days).
- Adverse events.
- Concomitant therapies.
- Schedule next visit.

8.5.4.5 Week 32 Visit

The following procedures will be conducted at the Week 32 Visit:

- Urine or serum pregnancy test (for female subjects of childbearing potential).
- Blood draws:
 - Creatinine.
 - CCI [REDACTED]
 - DSA.
 - C1-esterase inhibitor activity/antigen.
 - Immunoglobulin concentration.

NOTE: All blood draws should be completed before administration of investigational product and IVIg.

- Subcutaneous administration of blinded investigational product (C1-INH [60 IU/kg] or placebo, dose rounded to the lowest 1 mL).
- Investigational product dispense, if applicable.
- Investigational product vial return, if applicable.
- IVIg may begin if DSA is \geq 2000 MFI (2 grams/kg total dose; the dose must be administered over a minimum period of at least 2 days, and may be administered over a period of up to 5 days).
- Adverse events.
- Concomitant therapies.
- Schedule next visit.

8.5.4.6 Week 38 Visit/End of Treatment Period 2 Visit

The following procedures will be conducted at the Week 38 Visit:

- EQ-5D-3L questionnaire.
- Physical examination.
- Vital Signs.
- Pregnancy test (for female subjects of childbearing potential).
- Blood draws:
 - Creatinine.
 - Serum pregnancy test (for female subjects of childbearing potential).
 - Serum biochemistry panel.
 - Hematology.

- CCI [REDACTED]
- DSA.
- C1-esterase inhibitor activity/antigen.
- CCI [REDACTED]
- Retention sample for viral serology.
- CCI [REDACTED]

NOTE: All blood draws should be completed before administration of investigational product.

- CCI [REDACTED]
- Biopsy of kidney allograft.
- Subcutaneous administration of blinded investigational product (C1-INH [60 IU/kg] or placebo, dose rounded to the lowest 1 mL).
- NOTE: This is the final dose of blinded investigational product administered as a part of TP2.
- Investigational product vial return, if applicable.
- Adverse events.
- Concomitant therapies.
- Schedule next visit.

8.5.5 Responder Follow-up Period

Throughout the Responder Follow-up Period:

- Assessment of DSA and/or allograft biopsy will be conducted as per local standard of care. If the investigator becomes aware of an AE that has started after the observation period has finished, and there is at least a possible causal relationship to the investigational product, the event must be reported to CSL (see [Section 9.4](#)).

8.5.5.1 Month 12 Visit

The following procedures will be conducted at the Month 12 Visit:

- EQ-5D-3L questionnaire.
- Blood draws:

- Creatinine.
- CCI [REDACTED].
- C1-esterase inhibitor activity/antigen.
- CCI [REDACTED]
- Allograft failure (yes/no).
- Subject survival (yes/no).
- Development of biopsy-confirmed AMR since the last visit (yes/no).
- Schedule next visit.

8.5.5.2 Month 18, Month 24, Month 30, Month 36, and Month 42 Visits

The following procedures will be conducted at the Month 18, 24, 30, 36, and 42 Visits:

- EQ-5D-3L questionnaire (Month 24 and 36 Visits only).
- Blood draws:
 - Creatinine.
- Allograft failure (yes/no).
- Subject survival (yes/no).
- Development of biopsy-confirmed AMR since the last visit (yes/no).
- Schedule next visit.

8.5.5.3 Month 48 Visit/End of Study Visit

The following procedures will be conducted at the Month 48 Visit, or if a subject withdraws from the study during the Responder Follow-up Period:

- EQ-5D-3L questionnaire
- Blood draws:
 - Creatinine.
 - CCI [REDACTED].
- Allograft failure (yes/no).
- Subject survival (yes/no).
- Development of biopsy-confirmed AMR since the last visit (yes/no).
- Serious Adverse Events.

8.5.6 Retreatment Period(s)

- Subjects may undergo retreatment during the Responder Follow-up Period with the blinded investigational product to which they were randomized in TP2. Retreatment may occur following a diagnosis of persistent or recurrent AMR by biopsy, evidenced by infiltrating neutrophils and/or monocytes with or without the presence of C4d ($g > 0$, $v > 0$, and/or $ptc > 0$; if C4d is negative, $g + ptc \geq 2$).
- Retreatment may start at any time during the Responder Follow-up Period, and will last for 25 weeks or until the Month 48 Visit, whichever occurs first. The Retreatment Period may also be shorter than 25 weeks at the investigator's discretion.
- If retreatment is stopped prior to completing the entire Retreatment Period, the procedures at the Retreatment Week 26 visit should replace the procedures at the scheduled monthly visit.
- Subcutaneous investigational product (ie, C1-INH or placebo) will be administered every 3 or 4 days (ie, twice weekly) during a Retreatment Period.
- Assessment of DSA will be conducted as per local standard of care.

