 - Scheduled study visits occurring during the first 2 weeks of the open-label Treatment Period 1 (TP1) will be referenced using days (eg, the Day 1 Visit, the Day 14 Visit, etc).
 - Scheduled study visits occurring after the first 2 weeks of the open-label TP1 and during the blinded Treatment Period 2 (TP2) will be referenced using weeks (eg, the Week 3 Visit, the Week 12 Visit, the Week 38 Visit, etc).
 - Scheduled study visits occurring during the Responder Follow-up Period will be referenced using months (eg, the Month 12 Visit, the Month 48 Visit, etc).
 - Scheduled study visits occurring during the first week of a Retreatment Period will be referenced using days and will be designated as retreatment visits (ie, the Day 1 Retreatment Visit and the Day 7 Retreatment Visit). Scheduled study visits occurring after the first week of a Retreatment Period will be referenced using weeks and will be designated as retreatment visits (eg, the Week 2 Retreatment Visit, the Week 22 Retreatment Visit, etc).
- For the purposes of the conduct of this study, the following equivalencies will be used:
 - 24 hours is equal to 1 day.
 - 1 week is equal to 7 days.
 - 1 month is equal to 28 days.
 - 52 weeks is equal to 1 year.
- In this protocol, the term ‘therapy’ (eg, prior and/or concomitant therapy) is inclusive of any intervention, medication, or other treatment that a subject may receive.

1 Introduction

[figure not shown]

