3.2 Dose and Dosing Regimen

Table 10 Summary of Administration of Investigational Product

Timeframe	Intravenous Administration	Subcutaneous Administration
Treatment Period 1: The Day 1 Visit to the Day 13 Visit ^a	60 IU/kg C1-INH	Not applicable
Treatment Period 1: The Day 14 Visit to the Week 12 2 nd dose ^a	Not Applicable	60 IU/kg C1-INH
Treatment Period 2: Week 13 to the Week 38 Visit ^b	Not Applicable	60 IU/kg C1-INH OR 0.12 mL/kg placebo
Retreatment Period: The Retreatment Day 1 Visit to the Retreatment Week 26 Visit ^c	Not Applicable	60 IU/kg C1-INH OR 0.12 mL/kg placebo

IV = intravenous; SC = subcutaneous

^a Treatment Period 1 is open-label and each subject will receive C1-INH. C1-INH (60 IU/kg) will be administered IV to each subject over the first 13 days of Treatment Period 1 for a total of 5 doses. Thereafter, C1-INH (60 IU/kg twice weekly) will be administered SC to each subjects for the remainder of Treatment Period 1. The first dose of randomized investigational product will be administered to responders at the Week 13 Visit.

^b Treatment Period 2 is blinded and subjects will be randomized 1:1 to treatment with investigational product (C1-INH [60 IU/kg] or placebo) subcutaneously twice weekly.

^c Retreatment Period(s) are blinded and subjects will receive the same investigational product treatment assignment as received during Treatment Period 2.

Note: Week 13 is the final visit of Treatment Period 1 for non-responders and the first visit of Treatment Period 2 for responders.

Treatment Period 1

C1-INH will be administered to all subjects during TP1 in an open-label manner.

C1-INH will be administered intravenously to subjects at the Day 1, 4, 7, 10, and 13 Visits for a total of 5 doses. Intravenous C1-INH will be administered at the study site during site visits.

Subcutaneous C1-INH will be administered every 3 to 4 days (ie, twice weekly) beginning at the Day 14 Visit and for the remainder of TP1. Subcutaneous C1-INH is required to be administered at the study site during site visits, but at other times may instead be administered at home by a medical professional (eg, a home visit nurse) or by the subject under the supervision of a medical professional.

Treatment Period 2

Investigational product (ie, C1-INH or placebo) will be administered to all subjects during TP2 in a double-blind manner.

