Subcutaneous investigational product will be administered every 3 to 4 days (ie, twice weekly) during TP2. Subcutaneous C1-INH is required be administered at the study site during site visits, but at other times may instead be administered at home by a medical professional (eg, a home visit nurse) or by the subject under the supervision of a medical professional.

Retreatment Period

Subjects may undergo retreatment during the Responder Follow-up Period with the blinded investigational product to which they were randomized in TP2. Retreatment may occur following a diagnosis of recurrent or persistent AMR by biopsy, evidenced by infiltrating neutrophils and/or monocytes with or without the presence of C4d (glomerulitis [g] > 0, intimal arteritis [v] > 0, and/or peritubular capillaritis [ptc] > 0; if C4d is negative, g+ptc \geq 2). Retreatment may start at any time during the Responder Follow-up Period, and will last for 26 weeks or until the Month 48 Visit, whichever occurs first. The Retreatment Period may also be shorter than 26 weeks at the investigator's discretion.

During the Retreatment Period, SC investigational product will be administered twice weekly (approximately every 3 to 4 days). During the Retreatment Period (if needed), SC C1-INH will be administered either at the site or may be dispensed to the subject and administered SC at home either by a medical professional or by the subject under the supervision of a medical professional.

Subcutaneous Administration of the Investigational Product

Subcutaneous administration of the investigational product should be via a single SC injection in the abdomen, thigh, upper arm, or other appropriate location. The injection site should be changed for each new administration and should be at least 5 cm (2 inches) away from the previous injection site.

The twice weekly administration of investigational product beginning at the Day 14 Visit and during any Retreatment Period (if applicable) should ideally be scheduled on fixed days of the week (eg, Monday and Thursday). The suggested interval between each administration of investigational product is 3 or 4 days (ie, twice weekly). In addition, the investigational product should ideally be administered at approximately the same time on each day. A missed

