5.4 Other Intervention(s)

5.4.1 Intravenous Immunoglobulin

During the open-label TP1, IVIg will be administered every 4 weeks at a dose of 2 grams/kg. The dose must be administered over a minimum period of at least 2 days, and may be administered over a period of up to 5 days. The administration of IVIg will begin on Study Day 1 with the following exceptions:

1. For subjects who have received their last dose of IVIg < 1 gram/kg as part of standard of care within the 2 weeks before Study Day 1 OR
2. For subjects who have received their last dose of IVIg ≥ 1 gram/kg as part of standard of care within the 4 weeks before Study Day 1

For these subjects, the administration of IVIg will begin on the Week 4 Visit.

During TP2 and Retreatment Period, IVIg may be administered if $DSA \geq 2000$ mean fluorescence intensity (MFI) based on the clinical judgement of the investigator.

The complete schedules for IVIg dosing during TP1, TP2, and any Retreatment Period are presented in [Table 1](#), [Table 2](#), and [Table 5](#), respectively.

All blood draws scheduled for the same visit as IVIg dosing should be taken BEFORE the initiation of IVIg dosing.

If a scheduled dose of IV C1-INH is the same day as IVIg administration, it should be administered AFTER the IVIg dose. Subcutaneous C1-INH may be administered during an IVIg infusion.

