8.1.3.3 Renal Allograft Biopsy

Inclusion Biopsy

The renal allograft biopsy used to determine inclusion into the study will have been performed as standard of care within 90 days before the Day 1 Visit. The diagnosis of AMR can be made > 90 days before Day 1 as long as the inclusion biopsy establishes that AMR is ongoing within 90 days of Day 1. Slides stained with hematoxylin and eosin stain, periodic acid-Schiff, trichrome stain, and silver stain or will be provided to the central histopathologist for evaluation as the baseline for comparison with the Week 38 biopsy.

Week 38 Biopsy

A biopsy will be performed at Week 38 (ie, the End-of-TP2), and will be compared to the inclusion biopsy to assess changes in histopathology. Where possible, a biopsy should also be performed for subjects who discontinue treatment before the Week 38 Visit. The central histopathologist will be blinded to treatment assignment beginning with TP2.

Biopsy during the Responder Follow-up Period

Subjects may have additional biopsies as part of their local standard of care treatment at any point during the study, including during the Responder Follow-up Period. A biopsy at the Week 38 Visit or during the Responder Follow-up Period that shows evidence of infiltrating neutrophils and/or monocytes with or without the presence of C4d ($g > 0$, $v > 0$, and/or $ptc > 0$; if C4d is negative, $g + ptc \geq 2$) will qualify as an episode of acute AMR (see [Appendix 3](#)). A subject with a biopsy-proven persistent or recurrent episode of AMR may receive additional treatment according to their previous randomization (C1-INH or placebo) in addition to monthly IVIg (2 grams/kg) ([Table 5](#)). Slides of any biopsy taken during the Responder Follow-up Period documenting a persistent or recurrent episode of AMR will be provided to the central histopathologist.

Histopathology

Representative histopathology sections from each renal allograft biopsy will be processed with hematoxylin and eosin stain, periodic acid-Schiff, trichrome stain, and silver stain. In addition, frozen or formalin fixed biopsy sections will be processed for the presence of C4d by any immunoassay.

In addition, any electron micrograph images (if available) from representative allograft biopsies should be sent to the central repository for the study pathologist.

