8.5.6.6 Retreatment Week 26 Visit

The following procedures will be conducted at the Retreatment Week 26 Visit:

- Physical examination.
- Vital signs.
- Blood draws:
 - Creatinine.
 - Retention sample for viral serology.
 - Serum pregnancy test (for female subjects of childbearing potential).

NOTE: All blood draws should be completed before administration of C1-INH.

- Subcutaneous administration of blinded investigational product (C1-INH [60 IU/kg] or placebo, dose rounded to the lowest 1 mL).
- Investigational product vial return, if applicable.
- Adverse events.
- Concomitant therapies.
- Schedule next visit.

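### The protocol gives the Retreatment Period as both 25 and 26 weeks and states two different IVIg rules for it; the passages need to be reconciled (minor)

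*Protocol*

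**What the plan says.** **Duration.** Protocol 8.5.6 and Table 5 Note 1 say that retreatment "will last for 25 weeks or until the Month 48 Visit, whichever occurs first". Protocol 3.2 and SAP 4.3 say that it "will last for 26 weeks or until the Month 48 Visit, whichever occurs first". The clause that lets the investigator shorten the course also differs: it refers to 25 weeks in the first pair and 26 in the second. The dosing tables (synopsis, Protocol Table 10, SAP Table 4) run from "The Retreatment Day 1 Visit to the Retreatment Week 26 Visit". Table 5 places that last visit on Day 182 with a window of 7 days either side. The procedures for it in 8.5.6.6 include "Subcutaneous administration of blinded investigational product (C1-INH [60 IU/kg] or placebo, dose rounded to the lowest 1 mL").

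**IVIg.** Protocol 8.1.3.3 says that a subject with biopsy-proven persistent or recurrent AMR may receive further treatment "according to their previous randomization (C1-INH or placebo) in addition to monthly IVIg (2 grams/kg"), with a reference to Table 5 and no DSA condition. Section 5.4.1 reads "During TP2 and Retreatment Period, IVIg may be administered if" DSA is at least 2000 MFI, on the investigator's clinical judgement. Figure 1 footnote c, Table 5 footnote g and the visit lists in 8.5.6.1 and 8.5.6.3 to 8.5.6.5 carry the same threshold. Footnote c also gives a four-week interval.

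**DSA.** Table 5 Note 3 and Section 8.5.6 leave DSA testing during retreatment to local standard of care. No retreatment visit lists a DSA draw.

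**The concern.** These are treatment instructions in current text. A site that works from 8.5.6 and one that works from 3.2 would plan different last doses. A site that reads 8.1.3.3 alone would see monthly IVIg as part of retreatment, while one that reads 5.4.1 would see an option that depends on a laboratory value. In TP2 the same threshold is supported by a DSA draw at every visit where IVIg may begin. In retreatment it has no scheduled result behind it.

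What is at stake is consistent retreatment exposure and a clear meaning of a completed course. Section 8.5.6 has the Week 26 procedures replace a scheduled visit when retreatment stops before the whole period is completed. A subject who stops on Day 175 has finished under one sentence and stopped early under the other. The question was live at termination: SAP Section 3 reports one subject still in retreatment and ties database lock to completion of that subject's dosing regimen.

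**Working it through.** **Inputs.** The Conventions section of the protocol sets "1 week is equal to 7 days" and one month to 28 days. Table 5 places the retreatment visits on Days 1, 7, 28, 56, 84, 112, 154 and 182. Investigational product is given twice weekly at 60 IU/kg or matching placebo volume.

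**Step 1: reproduce Table 5.** 26 × 7 = 182, so Week 26 = Day 182 holds. The others agree: 28/7 = 4, 56/7 = 8, 84/7 = 12, 112/7 = 16, 154/7 = 22.

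**Step 2: can 25 and 26 both be right?** A 25-week course ends at 25 × 7 = Day 175. Day 1 to Day 182 is 181 elapsed days (181/7 = 25.9 weeks), or 182 days counted inclusively (26.0 weeks). Only subtracting visit labels (26 − 1) gives 25, and that cannot explain one sentence printed with two numbers. TP2 does last 25 weeks by its labels (38 − 13 = 25), but its first dose is at Week 13, whereas retreatment starts on Day 1.

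**Step 3: size of the duration gap.**

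| | 25 weeks | 26 weeks | Difference |
|---|---|---|---|
| Days | 175 | 182 | 7 |
| Doses at 2 per week | 50 | 52 | 2 |

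Two doses are 2 × 60 = 120 IU/kg in the C1-INH arm, before rounding. Day 175 is also 182 − 7, the lower edge of the visit window.

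**Step 4: IVIg rule, side by side.**

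| Place | Condition | Interval |
|---|---|---|
| Protocol 8.1.3.3 | none stated; cites Table 5 | monthly (28 days) |
| Protocol 5.4.1 | optional, DSA ≥ 2000 MFI | refers to Table 5 |
| Figure 1 footnote c | optional, DSA ≥ 2000 MFI, local laboratory | every 4 weeks |
| Table 5 footnote g | optional, DSA ≥ 2000 MFI | at marked visits |
| 8.5.6.1, 8.5.6.3 to 8.5.6.5 | optional, DSA ≥ 2000 MFI | Day 1, Weeks 4, 8, 12, 16, 22 |

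**Step 5: interval.** Gaps between the listed IVIg visits are 27, 28, 28, 28 and 154 − 112 = 42 days. The last is six weeks and fits neither the monthly nor the four-week wording. As extracted, Table 5 marks IVIg at Day 1 and Weeks 4, 8, 12 and 16 but not Week 22. I give that little weight, because other rows of the extracted table, such as physical examination, also fail to line up with the visit lists. The mismatch between Weeks 16 and 22 and footnote c does not depend on the table.

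**The case against.** The best defence is that this is loose drafting around a workable scheme. The duration gap is one week at most and lies within the visit window, and both versions let the investigator stop sooner. Section 8.1.3.3 is a biopsy section, uses permissive wording and points to Table 5, whose footnote carries the DSA condition. Every other IVIg passage agrees with that footnote. The threshold uses local results, so leaving DSA to local practice is coherent, and an investigator who considers IVIg can order the test.

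Much of this stands, and it limits the size. It does not remove the conflict: the two duration sentences cannot both be followed, 8.1.3.3 describes IVIg without the condition, and nothing in Table 5 ensures a DSA result to apply it.

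A reader might infer more than the documents support:

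- **IVIg is mandated monthly for all retreated subjects.** The text says that a subject may receive it and cites Table 5.
- **Planned retreatment volume is undefined.** SAP 11.1 counts planned twice-weekly doses from the dosing start and end dates, and SAP 8.2.9 takes the retreatment start and end from documented intake. The nominal duration does not enter.
- **The adverse-event window is ambiguous.** Protocol 9.4 and SAP 8.3.1 run it to 30 days after the actual last dose.
- **The IVIg conflict is worth 0 against 12 g/kg** (six listed visits × 2 g/kg). All six entries are themselves conditional, so that range already exists within the DSA rule and does not measure its difference from 8.1.3.3.

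**Conclusion.** The protocol contradicts itself on the length of retreatment and on the conditions and interval for IVIg during it, so sites could manage the same relapse differently. It does not follow that they would, because both the length of the course and the use of IVIg are open to investigator discretion. Severity is minor. The duration gap is at most 7 days and 2 doses per course, assuming a full course at the stated frequency. No gram-per-kilogram figure can be put on the IVIg conflict from the documents.

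A reader might also infer harm to the efficacy conclusions. Retreatment takes place in the Responder Follow-up Period, after TP2, so the primary endpoint is unaffected. SAP Section 5 no longer analyses the 48-month graft endpoints, and SAP 4.2.1.3 plans no formal testing.

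**What to change.** 1. Reconcile Table 5 Note 1, Protocol 3.2 (text and Table 10), 8.5.6, 8.5.6.6 and SAP 4.3 to one duration and one last-dose visit, with the early-stopping clauses to match.
2. Reconcile Protocol 8.1.3.3 with 5.4.1, Figure 1 footnote c, Table 5 with its footnote g, 8.5.6.1 and 8.5.6.3 to 8.5.6.5 to one IVIg rule and one interval, including the Week 16 and Week 22 entries.
3. Make Table 5 consistent with whichever IVIg rule is kept. If that rule depends on DSA, the schedule should show whether a result is available to apply it.

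Which duration and which IVIg rule apply is for the sponsor to decide. SAP 11.1 needs no change on this account. The cost is a protocol clarification and a matching line in SAP 4.3, with no extra subjects.
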